^{c.} At Screening ECGs will be performed in a standardized method, in triplicate, and approximately 30 seconds apart, prior to blood draws or other invasive procedures. Single ECGs will be performed from Day 1 to EOS.

^{d.} A serum pregnancy test will be performed at screening. Serum or highly sensitive urine (cutoff of 20 mlU/L) pregnancy tests will be performed at Day -1, Day 8 Pre-Dose and EOS.

^{e.} Flexible PK sampling point, that could be collected at any time on Day 8 between pre-PACAP-38 to 2 hours post-PACAP-38 administration.

^{f.} PACAP-38 should not be administered if subject reports having a headache within 72 hours prior to Day 8. Subject should return to the research facility from Day 8 – Day 12 for PACAP-38 administration.

⁹ Rectal temperature will be collected after obtaining blood pressure, prior to PACAP-38 infusion and post PACAP-38 infusion at Hours 0.5, 2 and 24.

^{h.} Negative drug, alcohol and cotinine test is required prior to PACAP-38 dose. Positive results will be reviewed between the PI and MM on a case by case basis.

¹ Laboratory results required prior to AMG 334 and PACAP-38 dose. Abnormal lab results will be reviewed between the PI and MM on a case by case basis prior to PACAP-38 dose.

^{j.} A reliable urine drug test performed at the site is allowed.

^k Additional serum will be collected for an FSH, LH, or estradiol test for postmenopausal women at screening as defined in Section 7.2.22.

¹ Cardiac enzymes include CPK-MB and Troponin I or Troponin T.

	0		The first of Parts I					Follo	w-Up	EOS				
Activity	Screenin	ng										Per		VISIT
Study Day	-21 to -2	-1										Day 2	Day 3	Day 8
Time (in nours)			Pre-Dose	0	0.25	0.5	1	2	3	4	ð	24	48	
General & Safety Assessments	X	1	1			-	1	1		1			 	
Informed Consent	X				X		V	V	V	V	X			
Residency		-	X	X	X	X	Х	Х	Х	Х	Х	X		
Medical History	X													
Body Weight	X	X												X
Height	X		a a d					a d				d		
Vital Signs (BP, HR, RR, TEMP) ^u	Х	Х	Xu		Х	Χu	Х	Xu	Х	Х	Х	Χu	Х	Х
Physical Examination	Х	Х												Х
Neurological Examination	Х		Х									Х		Х
12-lead Electrocardiogram ^a	Х		Х			Х	Х	Х		Х	Х	Х	Х	Х
Adverse Event Recording				Х	Х	Х	Х	Х	Х	Х	Х	Х	Х	Х
Serious Adverse Event	Х	Х	Х	Х	Х	Х	Х	Х	Х	Х	Х	Х	Х	Х
Concomitant Medications	Х	Х	Х	Х	Х	Х	Х	Х	Х	Х	Х	Х	Х	Х
Laboratory Assessments														
Creatinine Clearance	Х	Х										Х		
Clinical Chemistry	Х	Х										Х		Х
Clinical Hematology	Х	Х										Х		Х
Urinalysis	Х	Х										Х		Х

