7.2 General Study Procedures

Any blood sample collected according to the Schedule of Assessments (Table 2 and Table 3) may be analyzed for any of the tests outlined in the protocol and for any tests necessary to ensure subject safety. This includes testing to ensure analytical methods produce reliable and valid data throughout the course of the study. This may also include, but is not limited to, investigation of unexpected results, incurred sample reanalysis, and analyses for method transfer and comparability.

Throughout the study, the permitted time windows for scheduled assessments will be as follows:

- +4 day for Day 1 For Non Randomized (PACAP-38 Only) Dose Selection Subjects Only
- + 4 day for Day 8 for Randomized (AMG 334 or Placebo) Subjects
- ± 30 minutes for Headache Questionnaire
- ± 3 days for Days 29, Day 57 and EOS (Day 8 for Non Randomized (PACAP-38 Only) Dose Selection Subjects and Day 85 for Randomized (AMG 334 or Placebo) Subjects)

If informed consent is provided by the subject, Amgen may do additional testing on remaining samples (ie, residual and back-up) to investigate and better understand neurological disorders, the dose response and/or prediction of response to AMG 334, characterize antibody response, and characterize aspects of the molecule. Results from this analysis will be documented and maintained, but may not be reported as part of this study.

Additional procedures deemed necessary as part of standard of care or as required by local laws and regulations may be performed at the Investigator's discretion.

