MLA and non-migraine headaches should be recorded on the headache questionnaires and on the adverse event eCRF page.

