
Primary Completion:

Defined as the time when the last subject is assessed or receives an intervention for the purposes of final collection of data for the primary analysis (ie., when the last subject completes the migraine questionnaire 24 hours after challenge agent (PACAP-38) administration or is discontinued from the study).

End of Trial:

Defined as the time when the last subject is assessed or receives an intervention for evaluation in the study (ie., when the last subject completes the study, which includes the safety follow-up visit 11 weeks after the challenge agent (PACAP-38) administration, or is discontinued from the study).

Statistical Analysis Plan: 20140207

Date: 17 May 2017 Page 16

Subject-level EOS Date

EOS for each subject is defined as the date the subject last participated in the study.

The date will be recorded on the EOS case report form (CRF) page.

Enrollment

A subject will be considered enrolled when the investigator decides that the subject has met all eligibility criteria. Enrollment Date is defined as the date collected on the CRF.

Investigational Product (IP)

The term IP is used in reference to AMG 334 or placebo.

PACAP-38

Pituitary adenylate cyclase-activating polypeptides-38 is a neuropeptide belonging to the VIP/secretin/glucagon superfamily. PACAP-38 is a non-investigational medicinal product (NIMP) and used as a challenge agent.

Randomization Date

The day the subject was assigned a randomization number.

Study Day 1

Day 1 is defined as the first day that IP is administered to the subject. The day before Day 1 is referenced as Day-1.

Study Day

Post day of dose: study day= (study date - date of study Day 1) +1

Pre day of dose: study day= (study date - date of study Day 1)

The day prior to the first IP dosing is Day –1 while the day of the first IP dose is Day 1.

7. Analysis Subsets

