10.6.2 Safety Endpoints

10.6.2.1 Adverse Events (AEs)

The Medical Dictionary for Regulatory Activities (MedDRA) version 19.1 or later will be used to code all AE to a system organ class and a preferred term. The subject incidence of AEs will be summarized for all treatment-emergent, serious treatment-emergent, those leading to withdrawal of IP, fatal, and events of interest (EOI), where treatment refers to IP. The identification of EOI is a continuous process. Events may be identified and documented as the safety profile of the drug is characterized. The severity of each AE will be graded using common terminology for AE (CTCAE) version 4.0 criteria.

Statistical Analysis Plan: 20140207

Date: 17 May 2017 Page 24

Subject incidence of all treatment-emergent, serious treatment-emergent, those leading to withdrawal of IP, and fatal AE will be tabulated by system organ class and preferred term, where treatment refers to IP. Where appropriate, the tables will also be presented by worst grade. The above AE tables will not be created if two or fewer subjects experience the AE. The above AE tables will be summarized separately for events occurring between Day 1 and Day 7 following administration of IP and events occurring from Day 8 onwards following administration of IP and the second dose of PACAP-38.

For PACAP-38 related treatment-emergent AEs, all treatment-emergent AEs where the question "Is there a reasonable possibility that the event may have been caused by PACAP-38?" is ticked "yes" will be summarized by treatment group.

Details of each AE will be listed.

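### The by-period adverse event tables are cut at study Day 7/Day 8, although the PACAP-38 challenge they are meant to separate may be given on any day from Day 8 to Day 12

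*SAP*

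**What the plan says.** SAP 10.6.2.1 asks for the treatment-emergent AE tables to be produced separately for two periods. The earlier table takes "events occurring between Day 1 and Day 7 following administration of IP". The later table, by contrast, takes "events occurring from Day 8 onwards following administration of IP and the second dose of PACAP-38".

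SAP section 6 fixes what a day number means. "Day 1 is defined as the first day that IP is administered to the subject", and later days follow from "Post day of dose: study day= (study date - date of study Day 1) +1". The count is by calendar date from IP and does not refer to PACAP-38.

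The supplied protocol does not tie the Part B challenge to Day 8. Table 2, footnote f, says "PACAP-38 should not be administered if subject reports having a headache within 72 hours prior to Day 8". For the deferred dose, the same footnote gives this range: "Subject should return to the research facility from Day 8 – Day 12 for PACAP-38 administration". Section 7.2 lists the matching visit window as plus "4 day for Day 8 for Randomized (AMG 334 or Placebo) Subjects".

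The design text in SAP 3.1 places the challenge on Day 8 and does not mention a window. The SAP has no rule for AEs in subjects whose challenge is deferred.

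**The concern.** Treatment-emergent AEs are a secondary endpoint. The two-period layout is the SAP's only time-based separation of experience on AMG 334 or placebo alone from experience after the challenge has been added. It does that job only if the boundary is the infusion. With a fixed boundary at Day 8, a subject infused later has days in the second period on which the post-IP PACAP-38 dose had not been given.

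The subjects concerned are not a random subset, because a recent headache is the protocol's stated ground for deferral. Protocol 9.2.2.1 adds that "MLA and non-migraine headaches should be recorded on the headache questionnaires and on the adverse event eCRF page", so a new headache during the wait can reach the AE tables, and it resembles what the challenge produces (headache was reported in 71.4% of the Cohort 1 to 3 subjects, protocol 2.4). Arms are small: at 8 per arm one subject is 1/8 = 12.5 percentage points, and at 18 per arm 1/18 = 5.6. A single misplaced event can therefore change how a by-period row looks.

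**Working it through.** **Inputs**
- Period boundary: Day 7/Day 8 (SAP 10.6.2.1).
- Day count: by date from IP, with the IP day as Day 1 (SAP section 6).
- Challenge window: Day 8 plus 4 days (protocol 7.2); Day 8 to Day 12 (Table 2, footnote f).
- AE timing: onset and resolution dates are the listed attributes, with no clock time (protocol 9.2.2.1).
- Infusion timing: start date and time are recorded on the eCRF (protocol 6.3.1.1).

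**Reproducing the protocol's figure.** 8 + 4 = 12, so section 7.2 and footnote f agree on the last permitted day.

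**Misplaced time.** For a subject infused on Day d, the full days between IP and challenge number d − 1 (Days 1 to d − 1). Those at or beyond the SAP boundary number d − 8 (Days 8 to d − 1).

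| Infusion day d | Pre-challenge days (d − 1) | Of these, on or after Day 8 (d − 8) | Share |
|---|---|---|---|
| 8 | 7 | 0 | 0% |
| 9 | 8 | 1 | 12.5% |
| 10 | 9 | 2 | 22.2% |
| 11 | 10 | 3 | 30.0% |
| 12 | 11 | 4 | 36.4% |

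The hours before infusion on the dosing day come on top, and they are affected even for a subject infused on Day 8. Against the period that receives them, the effect is smaller: Days 8 to 85 are 85 − 8 + 1 = 78 days, and 4/78 = 5%.

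**Where the events go.** The sentence can be read in two ways.
1. The words about IP and PACAP-38 describe the period that begins on Day 8. Pre-challenge events on Days 8 to 11 then enter the table labelled as following PACAP-38. The parallel wording of the first period favours this reading.
2. An event must be both on or after Day 8 and after the second PACAP-38 dose. The same events are then too late for the first table and too early for the second, and appear in neither.

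**Chance that a deferred subject contributes an event.** The documents give no AE rate for these days. As an assumption only, with a constant daily chance r of an AE onset and independent days, a subject infused on Day 12 has a chance 1 − (1 − r)^4 of at least one onset on Days 8 to 11: 7.8% for r = 0.02, 18.5% for r = 0.05 and 34.4% for r = 0.10. The range shows the sensitivity to r and is not an estimate for this trial.

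**The case against.** The strongest counter-arguments, and what stands of each:

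- **Version.** The window is in the supplied protocol dated 01 September 2016 (Amendment 3). The SAP states that it follows Amendment 4 (21 October 2016), which redesigned Part B and was not supplied. This stands as a condition: the sponsor must confirm that the window was kept.
- **Windows rule.** SAP 10.1 uses scheduled time points, including protocol windows, when data are summarized by time, so Day 8 might mean the challenge visit whenever it occurs. But that rule concerns values recorded against scheduled time points. AEs carry onset dates, and SAP section 6 defines study day by date. The rule does not clearly move the cut.
- **Equal observation.** A fixed seven-day first period gives every subject the same exposure. A cut at the infusion makes it 7 to 11 days, depending on something that happens after randomization. This is a genuine cost and is dealt with in the fix.
- **Limited reach.** Overall incidence is unchanged and every AE is listed. In these tables treatment means IP, and PACAP-38-related events have their own table based on the investigator's causality answer. The primary and headache endpoints are timed from the infusion, and SAP 10.1 describes model output as descriptive. All of this stands.

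Two stronger inferences are tempting and are not supported. One is that spontaneous headaches would be attributed to PACAP-38: attribution is made event by event elsewhere, and the headache that triggers deferral mostly falls on Days 5 to 7 and is correctly placed. The other is to take the chance of deferral as the error rate. With 1 to 5 migraine days in an assumed 30-day month and independent days, the chance of a migraine day in the 72-hour look-back is 1 − (1 − 1/30)^3 = 9.7% to 1 − (1 − 5/30)^3 = 42.1%. That describes who might be deferred. A misplaced event needs a new AE during the wait, and it is unclear whether every spontaneous migraine is recorded as an AE, since protocol 9.2.1 treats migraine as disease-related unless it worsens.

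**Conclusion.** The concern holds in a limited form. As written, the cut in SAP 10.6.2.1 is not tied to the challenge, and no other rule in the SAP repairs it. For a deferred subject, up to 4 full pre-challenge days, 4 of 11 at most, are labelled as post-challenge or dropped from both tables, depending on how the sentence is read. The rule is defective under either reading.

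The effect is confined to the by-period AE tables. The number of misplaced events cannot be derived from the documents. A difference between arms is possible if AMG 334 reduces spontaneous headache and so deferral, but nothing supplied shows it. The conclusion assumes that the Day 8 to Day 12 window survives in Amendment 4; it does not rest on any assumed headache or AE rate. The change should be made because the tables would otherwise not show what their labels say and the correction is nearly free. It is not a threat to the trial's main conclusions.

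**What to change.** Confirm that Amendment 4 keeps the Day 8 to Day 12 window. Then amend SAP 10.6.2.1 as follows:

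1. Period 1 runs from IP administration to just before the subject's actual post-IP PACAP-38 start. Period 2 runs from that start to end of study.
2. Challenge-day AEs are assigned by onset time where one is available. Where only a date is recorded, they go to period 2 by a stated convention. The causality answer should not decide the period, because that would replace timing with judgement.
3. Subjects who receive IP but are never challenged are handled as SAP section 11 already says: reviewed, not summarized.
4. Days at risk in each period are reported by arm, because period 1 will then vary from about 7 to 11 days.

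The cost is a few sentences in the SAP, one changed cut variable in the AE program and a small exposure summary. The infusion start date and time are already collected, so no new data are needed.

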10.6.2.2 Vital Signs

Vital signs will be reviewed for each subject. Summaries of HR and BP data over time and change from baseline will be provided. Depending on the size and scope of change in other vital signs, summaries may be provided.

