If the PI, MM, and GSO or designee decide not to proceed with enrollment into a subsequent cohort, then a Safety Review Meeting or DLRM will be held after the last dosed cohort. Refer to Section 10.4.2 for additional information on the Safety Review Meetings and DLRMs. The Safety Review Meeting or DLRM voting members will decide whether or not to proceed with enrollment in Part B Randomization (AMG 334 or Placebo) Phase and if the decision is made to proceed, the Safety Review or DLRM voting members will select the appropriate PACAP-38 dose. The decision to proceed with Part B of the study will be based on the goal of ensuring subject safety and ideally triggering headache in all subjects within a given cohort and moderate to severe MLAs in the majority of subjects within a given cohort and mild, moderate or severe MLAs in the majority of subjects within the same cohort may be considered acceptable to advance to Part B of the study.

All available study data, including the headache questionnaires, demographics, investigational product administration, medical history, concomitant medications, adverse events (including MLA), ECGs, vital signs, and laboratory results will be reviewed. Data to be reviewed at the DLRMs during the PACAP-38 Dose Selection Phase will not be blinded. Data to be reviewed for any unscheduled DLRM post the PACAP-38 Dose Selection Phase will be reviewed blinded (ie, treatment assignment will not be revealed) unless unblinding is deemed necessary for the review team to make

dosing decisions. If deemed necessary, unblinding will be performed to assist dose decisions in accordance with Amgen standard procedures.

6.3.1.3 PACAP-38 - Dosage Adjustments, Delays, Rules for Withholding, or Restarting Stopping or Permanent Discontinuation

Dosing of PACAP-38 will be stopped or modified by the DLRM voting members if suspected unexpected treatment related adverse events of Grade 2 or greater in the same system organ class occur in 2 or more subjects or Grade 3 occur in 1 or more subject. Dosing of PACAP-38 will also be stopped or modified by the DLRM voting members under the following circumstances:

- a) Blood pressure:
 - a. Systolic BP > 150 mm Hg OR
 - b. Diastolic BP > 100 mm Hg OR
 - c. Decrease in SBP from baseline > 30 mm Hg OR
 - Decrease in DBP from baseline > 15 mm Hg and considered clinically relevant after consultation between the investigator and the medical monitor.

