6.9 Excluded Treatments and/or Procedures During Study Period

Use of any over-the-counter or prescription medications within the 14 days or 5 half-lives (whichever is longer), prior to receiving the first dose of AMG 334 or PACAP-38. Simple

analgesics including NSAIDs will be allowed, but not within 48 hours prior to infusion of PACAP38. Subjects are not allowed to be on preventive therapies for migraine.

Paracetamol (up to 2 g per day) for analgesia and hormone replacement therapy (eg, estrogen, thyroid) will be allowed. Simple analgesics including NSAIDs will be allowed, but not within 48 hours prior infusion of PACAP-38. Subjects are allowed to take rescue medication for a migraine attack (their usual migraine treatment or a triptan) and for adverse events, such as emesis and allergic reactions (clemastin 2 mg, prednisolone 100 mg). Any herbal medicines (eg, St. John's wort), vitamins, and supplements consumed by the subject within 21 days prior to receiving the first dose of AMG 334, and continuing use if applicable, will be reviewed by the investigator and the Amgen Medical Monitor. Written documentation of this review and Amgen acknowledgement are required for subject participation. Refer to Section 6.5 for guidance on concomitant therapy.

- 7. STUDY PROCEDURES
- 7.1 Schedule of Assessments

Activity	Screeni	ng	Treatment Period											Fo	EOS Visit					
Study Day	-21 to -2	-1	Day 1 ^a						Dav	Day 9	Day 10	Day 29	Day 57	85						
Time (in hours)			Pre- Dose	0	0.5	1	Pre- Dose	0	0.25	0.5	1	2	3	4	8	24	48			
General & Safety Assessments	F	1	1	1	1		1				٩	I	1		1	I	٩	٩		
Informed Consent	Х						h													
Residency							X	Х	Х	Х	Х	Х	Х	Х	Х	Х				
Medical History	X																			
Body Weight	X	Х																		Х
Height	Х						~			~		~				~				
Vital Signs (BP, HR, RR, TEMP) ^g	X	Х	Х		Х	Х	X ^g		Х	X g	Х	Xg	Х	Х	Х	Xg	Х	Х	Х	Х
Physical Examination	Х	Х																Х		Х
Neurological Examination	Х		Х				Х									Х		Х		Х
12-lead Electrocardiogram ^c	X		Х		Х		Х			Х	Х	Х		Х	Х	Х	Х			Х
Adverse Event Recording				Х	Х	Х	Х	Х	Х	Х	Х	Х	Х	Х	Х	Х	Х	Х	Х	Х
Serious Adverse Event	Х	Х	Х	Х	Х	Х	Х	Х	Х	Х	Х	Х	Х	Х	Х	Х	Х	Х	Х	Х
Concomitant Medications	Х	Х	Х	Х	Х	Х	Х	Х	Х	Х	Х	Х	Х	Х	Х	Х	Х	Х	Х	Х
Laboratory Assessments	-											-								
Creatinine Clearance ⁱ	Х	х					х									Х				
Clinical Chemistry	Х	Х					Х									Х				Х
Clinical Hematology	Х	Х					Х									Х				Х
Urinalysis '	Х	Х					Х									Х				Х

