7.2.10 Vital Signs

The following measurements must be performed: systolic/diastolic blood pressure, heart rate, respiratory rate, and temperature. The position selected for a subject should be the same that is used throughout the study and documented on the vital sign eCRF. Record all measurements on the vital signs eCRF. The temperature location selected for a subject should be the same that is used throughout the study and documented on the vital signs eCRF. Rectal temperature will be collected at the time points designated in Table 2 and Table 3. Vital signs (blood pressure, heart rate, respiratory rate, and temperature) will be recorded by the principal investigator or designee at time points specified in the Schedule of Assessments (Table 2 and Table 3).

Blood pressure will be measured in the following manner:

- Subjects should be lying in a semi-recumbent position quietly and comfortably for at least 5 minutes. The upper arm should be bare without constrictive clothing and supported at heart level.
- Three consecutive measurements separated by approximately 5 minutes must be taken to establish baseline (ie, pre-dose) systolic/diastolic blood pressure. The mean of the three measurements should be recorded.
- Any clinically significant decrease in blood pressure readings must be confirmed with three consecutive measurements taken approximately 5 minutes apart. The mean of the three measurements should be recorded.
- Caffeine and exercise should be avoided for at least 30 minutes prior to measurement.
- An appropriately sized cuff (cuff bladder encircling at least 80 percent of the arm) should be used to ensure accuracy. At least 2 measurements should be made and the average recorded.
- Neither the subject nor the observer (measurer) should talk during measurement.

Subjects should be lying in a semi-recumbent position quietly and comfortably for at least 5 minutes for respiration and heart rate assessments. Respiration will be assessed by a full minute count. Abnormal measurements may be repeated upon investigator discretion. Record all measurements on the vital signs eCRF.

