2.3 Exploratory

- To evaluate the reduction in severity of PACAP-38 induced migraine-like attacks and headaches by AMG 334
- To evaluate the duration of PACAP-38 induced migraine-like attacks and headaches by AMG 334
- To evaluate the safety and tolerability of a single intravenous (IV) dose of exogenous PACAP-38
- To evaluate CGRP and PACAP-38 levels in migraine patients

3. Study Overview

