4.2 Planned Covariates and Subgroups

Planned covariates consist of baseline measures. No subgroup analysis is planned.

5. Hypotheses and/or Estimations

A single dose of 140 mg IV of AMG 334 will inhibit MLAs in subjects challenged with PACAP-38.

6. Definitions

Adverse Event (AE)

Serious Adverse Event (SAE):

SAE determined by the flag indicating if the adverse events is serious on the AE eCRF page will include these that occur after signing the informed consent and up to and including end of study (EOS).

Treatment-Emergent AE:

A treatment-emergent AE is that occurs on or after the initial dose of investigational product (IP) as determined by the flag indicating if the AE started prior to the first dose on the AE eCRF and up to and including end of study.

Disease-Related AE:

Migraine will be considered a disease related event; however, worsening of migraines (ie. increased frequency and/or intensity) should be reported as an AE.

Baseline

Unless otherwise stated, baseline will be defined as the last assessment taken prior to the first IP (AMG 334 or placebo) administration (ie, Day 1 pre-dose or Screening if Day 1 pre-dose is not available).

Statistical Analysis Plan: 20140207

Date: 17 May 2017 Page 15

Change from Baseline:

The arithmetic difference between a post-baseline value and the baseline value:

Change (absolute) from Baseline = (Post-baseline Value – Baseline Value)

Change (percent) from Baseline = [(Post-baseline Value – Baseline Value) / Baseline Value] x 100

Body Mass Index (BMI)

BMI will be calculated as {weight (kg)/ [height (m)]²} in the clinical database.

Columbia Suicide Severity Rating Scale (C-SSRS)

The C-SSRS is a clinical rating of suicidal ideation and behavior. Refer to Appendix E and Appendix F in the protocol for complete details on the C-SSRS. The Baseline/Screening version of the C-SSRS will be administered at screening (Day -21 to -2), while the Since Last Visit version of the C-SSRS will be administered at the other time point(s) on the Schedule of Assessments. Reports of suicidal ideation with intent to act (endorse item 4 or 5) and reports of actual, aborted, or interrupted suicide attempts or a behavior preparatory for making an attempt indicate subjects at high risk for suicide. If such reports are identified, the investigator is to appropriately manage the subject in accordance with standard of care.

End-of-Study (EOS)

The EOS is the last planned clinical visit for each subject enrolled in this study.

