10.1 General Principles

Unless otherwise stated, data from PACAP-38 responders who go on to be randomized and receive IP will be summarized. Data from PACAP-38 non-responders, and data from

Statistical Analysis Plan: 20140207

Date: 17 May 2017 Page 22

PACAP-38 responders that do not receive IP, will not be included in the summaries, but will be reviewed.

Unless otherwise specified, data will be summarized using the safety analysis set, by actual treatment group (AMG 334 or Placebo).

Descriptive statistics will be provided for selected demographics, safety and PK data. Descriptive statistics on continuous measurements will include means, medians, standard deviations (and standard errors for post-baseline data), quartiles, and ranges, while categorical data will be summarized using frequency counts and percentages. Where statistical models are applied to the data, estimates of the differences/ratios, confidence intervals and corresponding p-values will be presented, as applicable. However, these are for descriptive and illustrative purposes only and to aid interpretation of the data; no formal statistical hypothesis testing will be performed.

When data are summarized by time, the values recorded against the scheduled time points, including any time windows specified in the protocol will be used.

When assessing minimum/maximum increases or decreases over the study, all assessments, including unscheduled assessments will be used.

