10.7.4 Plasma Concentration of PACAP-38 and CGRP

Summary statistics will be generated for plasma PACAP-38 and CGRP levels pre/post dosing with PACAP-38. Summaries will be produced by treatment group for the second dose of PACAP-38 (ie., the dose administered after administration of IP).

Statistical Analysis Plan: 20140207

Date: 17 May 2017 Page 26

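### HR and BP changes after the Day 8 PACAP-38 infusion are measured only from the Day 1 pre-treatment reading, so the spread of the acute PACAP-38 response is not reported

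*SAP*

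**What the plan says.** SAP Section 10.6.2.2 states: "Summaries of HR and BP data over time and change from baseline will be provided". It names no baseline of its own, so the default in SAP Section 6 applies: "baseline will be defined as the last assessment taken prior to the first IP (AMG 334 or placebo) administration". In practice that is the Day 1 pre-dose value, with Screening as the fallback. SAP Section 3.1 places PACAP-38 on Day 8 after treatment on Day 1. Protocol Section 7.2 allows that visit to run 4 days late.

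Protocol Table 2 (Part B) schedules HR and BP before dosing on Day 8 and at nine times from 0.25 h to 48 h after the infusion. SAP Section 10.1 says continuous data will be described by means, medians, "standard deviations (and standard errors for post-baseline data), quartiles, and ranges".

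One exploratory objective in SAP Section 2.3 is "To evaluate the safety and tolerability of a single intravenous (IV) dose of exogenous PACAP-38". Protocol Section 10.5.3.2 made Day 8 pre-dose the baseline for ECGs recorded after PACAP-38; SAP Section 11 drops that summary. SAP Section 10.6.2.1 splits the adverse event tables at Day 8, when PACAP-38 is given.

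**The concern.** PACAP-38 acts quickly on HR and BP, and Protocol Section 2.4 expects transient changes in both. Describing an acute response normally calls for a reference taken shortly before the challenge. The schedule collects one, but the change table does not use it. Every post-infusion change therefore mixes the response of interest with whatever happened to that subject's resting HR or BP since Day 1.

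With the ECG summary gone, this is the only committed numerical summary of the haemodynamic response to PACAP-38. Individual changes matter here as well as means: Protocol Section 6.3.1.3 frames part of the PACAP-38 safety limits as a change within a subject, for example "Decrease in SBP from baseline > 30 mm Hg". What is at stake is the quality of a descriptive safety summary.

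**Working it through.** The plan gives no figure that depends on this baseline, so there is none to reproduce.

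**Timing.** Day 8 − Day 1 = 7 days. With the Amendment 3 window, Day 12 − Day 1 = 11 days. The gap is longer if Screening has to serve as baseline.

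**Identity.** For each subject and each time after the infusion:

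(post − Day 1) = (post − Day 8 pre-dose) + (Day 8 pre-dose − Day 1)

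The first term on the right is the acute response and the second is the shift.

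**Rows affected.** Post-baseline HR/BP times in Table 2 are Day 1 at 0.5 h and 1 h (2), Day 8 pre-dose (1), 0.25, 0.5, 1, 2, 3, 4, 8, 24 and 48 h after infusion (9), and Days 29, 57 and 85 (3). The total is 15, of which 9 follow PACAP-38 within 48 h.

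**What can be recovered.** With the same subjects in each row, the mean acute response is the mean change at that time minus the mean change at Day 8 pre-dose. Its SD needs the covariance between the post-infusion and Day 8 pre-dose values, which no planned table reports. The median, quartiles and range of a difference do not follow from those of its parts.

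**Effect on mean and spread.** A shift of d common to all subjects moves every within-arm mean change by d and leaves the SD alone. Subject-level day-to-day variation inflates the SD.

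**Size, on assumed values only.** Take a reading as subject level + day effect (SD b) + within-day noise (SD e), with response SD s. For the seven same-day rows (0.25 h to 8 h):

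- SD of change from Day 8 pre-dose = √(2e² + s²)
- SD of change from Day 1 = √(2(e² + b²) + s²)

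Assume e = 3 bpm throughout the table:

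| s | from Day 8 pre-dose | from Day 1, b = 3 / 5 / 7 | inflation |
|---|---|---|---|
| 5 | 6.56 | 7.81 / 9.64 / 11.9 | 19% / 47% / 81% |
| 8 | 9.06 | 10.0 / 11.5 / 13.4 | 10% / 27% / 48% |
| 11 | 11.8 | 12.5 / 13.7 / 15.4 | 6% / 17% / 31% |

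At s = 8, b = 5 and 18 per arm, the SE is 9.06/√18 = 2.1 bpm against 11.5/√18 = 2.7 bpm. The expected range (3.64 × SD) is 33 bpm against 42 bpm.

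With noisier readings (e = 5, b = 3, s = 8) the SDs are √114 = 10.7 and √132 = 11.5, an inflation of only 8%. A simpler model with equal SDs at all times gives a ratio of √((1 − r₁)/(1 − r₂)). With a Day 1 correlation r₁ of 0.5 to 0.7 and a same-session correlation r₂ of 0.8 to 0.9, that is √(0.3/0.2) = 1.2 to √(0.5/0.1) = 2.2.

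At 24 h and 48 h a Day 8 reference is nearer in time, but under the first model it brings no gain in SD, because those readings carry a different day effect.

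**The case against.** The strongest reply is that the table does its own job correctly. It sits under the safety endpoints, and change from the untreated state is the right description of AMG 334 safety. The listed endpoint for PACAP-38 safety is related adverse events, which SAP Section 10.6.2.1 summarises. No endpoint is a quantified HR or BP response. All of that stands, and it is why the planned table should stay.

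Two apparent precedents for a Day 8 reference are weak. SAP Section 10.7.4 covers "plasma PACAP-38 and CGRP levels pre/post dosing with PACAP-38", but it defines no change from baseline, and Table 2 has no plasma PACAP-38 sample before treatment. Protocol Section 7.2.10 requires three readings that "must be taken to establish baseline (ie, pre-dose) systolic/diastolic blood pressure", but it is a measurement instruction and does not say which dose. The ECG rule is the one real analogue.

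A reader might infer more than the documents support:

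- *That the comparison of AMG 334 with placebo is biased.* A shift common to both arms cancels in the contrast. Only a real AMG 334 effect on resting HR or BP would differ by arm, and the prior studies described in Protocol Section 2.2.2 report no such pattern. No HR or BP test is planned.
- *That PACAP-38 stopping limits would be misapplied.* The limits are applied during conduct, on confirmed readings, and the diastolic fall must also be judged clinically relevant. The HR limit is a cohort mean, and absolute BP limits can be read from the values over time. SAP Section 10.6.2.2 also has vital signs reviewed for each subject.
- *That the inflation is known to be large.* The variances are assumed, they are for HR only, and no BP figure is available.

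Finally, the SAP implements Protocol Amendment 4, and only Amendment 3 is supplied. The visit schedule, window and ECG rule come from Amendment 3. The baseline definition, the HR/BP summary and the Day 1/Day 8 timing are all in the SAP, so the point does not depend on the missing version.

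**Conclusion.** The point holds as a low-priority improvement to a descriptive summary. As written, HR and BP changes after the Day 8 infusion are referred only to Day 1, and the spread of the acute PACAP-38 response is neither tabulated nor recoverable. Nine of the 15 post-baseline times are involved.

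The size is unknown. The range of about 6% to 81% in SD for the same-day rows reflects the assumed HR values, and other plausible assumptions give other ranges, so none of these figures is evidence about this trial. The primary analysis and the interim and final decision rules are not affected, and the arm contrast is not biased.

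**What to change.** Leave the Day 1-baseline table as planned, including its 0.25 h to 48 h rows. They show change from the untreated state under AMG 334 plus PACAP-38, which would otherwise be lost.

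In SAP Section 6, add a second baseline for one purpose: *for the table of HR and BP response to PACAP-38, baseline is the Day 8 pre-dose value.* In SAP Section 10.6.2.2, add a labelled table by arm of HR and BP change from that value at 0.25 h to 48 h after the Day 8 infusion, with the descriptive statistics of SAP Section 10.1.

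The cost is one derived variable and one table from data already scheduled, with no new visit or sample. Two baselines must be labelled clearly, and a subject without a Day 8 pre-dose reading drops out of the added table.
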